The intervention will consist of four weeks of BLT via therapy glasses (Retimer^{LTD}), and four weeks of sBLT, in randomized order, spaced out by a one-week wash-out (i.e. no treatment) period, to minimize carry-over effects. The sham treatment will be delivered using the same therapy glasses used for active treatment, by applying a neutral density filter film on the LED light, thus blocking 85% of the blue-green wavelength light. To avoid subjects potential awareness of placebo treatment (differences in light intensity between the active and sham treatment cannot be completely eliminated), subjects will be told that the study will test the effects of two different light intensities on the target symptoms. This is "deception" in that if the subjects were told there was a placebo treatment and a study treatment they would be able to discern the difference therefore they are being told there are 2 types of light instead in order to preserve the blind. Subjects will be instructed to self-administer light therapy at home using study-provided BLT glasses for 60 min each morning at the prescribed time (derived from habitual wake up time) during a period of 8 weeks. After the first 4 weeks, they will bring their equipment in and it will be altered to either active or sham treatment. During the light therapy subjects can engage in other activities such as reading or having breakfast, but will be told not to shower with the therapy glasses on. They will also be instructed to remain indoors during the 60-minute treatment. Subjects will be given an alarm which has been pre-programmed to go off at the BLT prescribed time unless they prefer to use their own alarm on their personal alarm clock or phone. Adherence will be monitored by fitting the therapy glasses with a light and motion sensor. They will be instructed to wear the wrist actigraph for the entire duration of the treatment. It will, however, be replaced at intervals along with the glasses to preserve battery life. Participants will undergo a further final assessment at week 13, which is 4 weeks after completion of the treatment.

Please upload a table of procedures if applicable.

The study procedures table must be completed for:

- All Greater than Minimal Risk (GTM) studies; and
- All Minimal Risk studies that use Standard of Care or Usual Care/Interventions.

| | |
|-------------------------------------|------------------|
| Name | Modified Date |
| Table of Procedures | 8/7/2020 3:00 PM |

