ID: Pro00003376

View: 4.1 Research study methods: analysis Plan

1.0 * Please describe the analysis plan for the study (it is acceptable to refer to the sponsor/multi-site protocol for section if applicable):

Primary Data Analysis: We will use R version 3.4. **SA1:** To assess the feasibility of the current design to measure the effect of BLT on sleep related functional impairment in CPAP-treated individual with OSA. We will describe the following components of feasibility: recruitment and participant flow, adherence, data completeness and participant burden, and time course of treatment effects (e.g. do carry-over effects require a longer wash out period or suggest that a two-arm between-subject RCT design would be more appropriate?). Our main outcome analyses will employ multi-level linear mixed models with sleep related functional impairment and depression as the dependent variable, treatment block (BLT vs. sBLT) as predictor of interest, treatment sequence as a covariate, and subject intercept as a random effect.

Bivariate and colinear relationships will be assessed and proxy variables may be created to adjust for variables that are strongly biased (>3 SD from the mean) or highly collinear with a model-pertinent variable. Covariates we will be assessing include demographics (age, sex, race), comorbid conditions, lifestyle behaviors (smoking, alcohol use, substance use), adherence to BLT treatment, adherence to CPAP, medications for treatment of depression, use of hypnotic medications, and healthcare utilization (number of inpatient/ER visits within the past year).

SA2: to test the effects of bright light therapy on sleep related functional impairment, quality of life and CPAP-resistant symptoms of sleepiness and depression during the four-week active treatment portion of the eight-week crossover study, compared to the four-week sham treatment portion. These exploratory analyses will include bivariate analyses comparing patient outcomes between treatment and sham time periods by utilizing repeated measures ANOVA for quality of life and the Friedman test for categorical variables. We will conduct multi-level mixed effects models of each outcome while adjusting for covariates as listed in the primary aim.

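### The exploratory SA2 and SA3 mixed models adjust for adherence to the glasses, which is measured during treatment; entered per period, it can bias the BLT–sham contrast

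*Combined protocol and SAP*

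**What the plan says.** The covariate list stands in section 4.1, under the primary aim (SA1). It opens with "Covariates we will be assessing include demographics (age, sex, race), comorbid conditions" and goes on to lifestyle behaviours, "adherence to BLT treatment, adherence to CPAP, medications for treatment of depression, use of hypnotic medications" and healthcare use. Under SA1 these variables are only to be assessed. The SA1 main model has "sleep related functional impairment and depression as the dependent variable", with "treatment block (BLT vs. sBLT) as predictor of interest, treatment sequence as a covariate, and subject intercept as a random effect"; adherence is not named in it.

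The SA2 and SA3 paragraphs are firmer. Both contain the sentence "We will conduct multi-level mixed effects models of each outcome while adjusting for covariates as listed in the primary aim". Neither limits the adjustment to a sensitivity analysis or to baseline values.

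Section 4 (Research Study Methods, item 1.0) says how adherence is obtained: "Adherence will be monitored by fitting the therapy glasses with a light and motion sensor". It also says "The sham treatment will be delivered using the same therapy glasses used for active treatment", so adherence can be recorded in both periods. Section 4.1 names adherence as a feasibility component as well: "recruitment and participant flow, adherence, data completeness and participant burden".

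SA2 and SA3 also include bivariate comparisons: repeated-measures ANOVA for quality of life and for the rhythm parameters, and a Friedman test for categorical variables.

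**The concern.** Adherence to the glasses arises after randomisation, and the assigned condition may change it. Section 4 concedes that the difference in light intensity between active and sham cannot be fully removed, so unequal wear is plausible, though nothing in the documents shows it. If a covariate is affected by treatment and related to the outcome, conditioning on it changes what the treatment coefficient estimates. It may remove the part of the effect that runs through adherence. It may also create a spurious effect when something else, such as a bad fortnight, drives both wear and symptoms. Either way the coefficient is no longer the effect of assignment to BLT versus sham, which is the comparison SA2 sets out to make.

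The SA1 model covers functional impairment and depression only. For sleepiness, quality of life and the rhythm parameters, the covariate-adjusted model is the only mixed model in the plan. Section 6 (item 4.0) says the pilot's statistics will inform the design of the larger trial, so a distorted contrast could be carried forward.

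**Working it through.** The plan gives no figure on this point: no power calculation, alpha, outcome SD or expected adherence. Only maximum enrolment, 25 (section 6, item 1.0), comes from the documents. Everything else below is assumed.

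**Step 1: coding.** Let d be a person's BLT-minus-sham difference in outcome and a the same difference in adherence. A covariate with one value per person cancels from d, so it cannot move the within-person contrast. A per-period covariate does not cancel; it enters as a.

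**Step 2: bias under per-period coding.** Regress d on a, with d and a each scaled to SD 1. Let δ be the mean of a and β the within-person slope, so that the adjusted estimate is mean(d) − β·δ. If the true effect is 0 and adherence does not itself cause the outcome (β comes from shared causes), then

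bias = −(δ × β).

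With β from 0.25 to 0.49:
- δ = 0: bias 0
- δ = 0.1: 0.1 × 0.25 = 0.025 to 0.1 × 0.49 = 0.049
- δ = 0.2: 0.050 to 0.098
- δ = 0.5: 0.125 to 0.245

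These are absolute sizes. The sign is negative if wear is higher on BLT and positive if it is higher on sham.

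**Step 3: simulated paired-difference regression.** 20,000 trials per cell, n = 25, true effect 0:

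| δ (SD) | Adjusted estimate, β = 0.25 / 0.49 | False-positive rate, β = 0.25 / 0.49 |
|---|---|---|
| 0 | −0.001 / 0.000 | 5.2% / 5.1% |
| 0.1 | −0.028 / −0.051 | 5.2% / 5.9% |
| 0.2 | −0.052 / −0.097 | 5.5% / 8.2% |
| 0.5 | −0.124 / −0.243 | 8.6% / 22.0% |

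Without adherence, the estimate is about 0 and rejection is 4.7% to 5.5%. With n = 20 and δ = 0.5, the adjusted rates are 7.8% / 17.8%.

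**Step 4: the plan's own model form.** Treatment, sequence and a random intercept, fitted by REML; 2,000 trials per cell, n = 25, assumed intraclass correlation 0.5. Adding per-period adherence gives estimates of 0.001 / 0.001, −0.024 / −0.052, −0.056 / −0.101 and −0.122 / −0.242 at δ = 0, 0.1, 0.2 and 0.5 (Monte Carlo SE 0.005). Adding person-mean adherence leaves the treatment estimate identical to the unadjusted one (largest difference below 1e-15).

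**Step 5: other mechanisms.** A second simulation used n = 24, 4,000 runs, residual SD 1 per period, and treatment shifting adherence by −0.5, 0, 0.5 or 1.0.
- Adherence purely a mediator, slope 0.3: bias +0.15, 0, −0.15, −0.29.
- True null with an unmeasured common cause: +0.15, 0, −0.15, −0.30.
- Both mechanisms, with a direct effect of 0.5: +0.30, 0, −0.30, −0.60.

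The model without adherence recovered the total effect to within about 0.01 throughout. In one illustrative data set, the mixed-model estimate was 0.0148 (SE 0.2845) without adherence. It was the same with either the person's mean or the person's active-period value, and −0.2611 with the per-period value.

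**The case against.** The strongest reply is that harm needs two things the plan does not state: per-period coding and unequal adherence. Read literally, adherence to BLT could mean one active-period value per person, which step 5 shows to be harmless. Both conditions make two-light-intensity instructions, the same glasses and the same daily duration common ground, so similar wear is quite possible. This stands: the bias is possible, not certain. But the same methods section calls the device BLT glasses throughout both periods, so the literal reading is not secure, and the choice between a harmless and a biasing coding is left open.

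Second, the list is one of candidates, and 25 people cannot support all of it. That is a fair description of SA1. The SA2 and SA3 sentences, however, commit to adjusting for the list.

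Third, the numbers rest on assumed slopes and adherence gaps, and 22% is the worst corner of the grid at full enrolment. With SD 1 and n = 25 the unadjusted standard error is 1/√25 = 0.20, so at a gap of 0.2 SD the bias (0.05 to 0.10) is at most half a standard error. This also stands; small gaps do little damage.

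Fourth, unadjusted analyses sit alongside. Quality of life and the rhythm parameters have repeated-measures ANOVA, and function and depression have the SA1 model. That reduces the consequence. No unadjusted test is named specifically for the sleepiness score, and the plan does not say which estimate prevails if the two disagree.

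Finally, SA3 is about mediation, where adherence may have a legitimate role. The proposed change reaches only models that estimate the BLT–sham effect, so mediation and adherence–response analyses remain open.

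**Conclusion.** The concern holds. The plan commits the SA2 and SA3 mixed models to a covariate list that includes a variable measured only after randomisation. If it is coded per period and adherence differs between conditions, the adjusted contrast is not the effect of assignment. Under the assumed slopes and a true null, the bias runs from nothing with equal adherence to about a quarter of an SD at a gap of 0.5 SD. The direction depends on which condition is worn more. Person-level coding removes the problem.

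The weight is moderate. The aims are exploratory, the study is a feasibility pilot of at most 25, and the SA1 main model is not stated to include adherence. The change is still worth making, because the estimates are intended for planning the larger trial. The plan gives no measurement time for CPAP adherence, antidepressants or hypnotics; baseline values would not raise this problem, and values taken during treatment would raise the same question.

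**What to change.** In section 4.1, remove glasses adherence from every model that estimates the BLT–sham effect, including the SA2 and SA3 mixed models. Report adherence by period and by condition as an SA1 outcome. If an adherence–response or adherence-adjusted analysis is wanted, present it as supplementary, label it exploratory and non-randomised, and state how adherence is coded. State when CPAP adherence, antidepressant use and hypnotic use are measured, and restrict those covariates to pre-randomisation values.

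The cost is analysis-plan wording only; no data collection or study procedure changes. The one loss is that the adherence-adjusted estimate moves to a supplementary analysis.

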SA1: to test the feasibility of Bright Light Therapy (BLT) to ameliorate sleep related functional impairment in CPAP-treated individuals with OSA. Hypothesis: BLT, delivered via therapy glasses, will have high rates of acceptance and adherence among Veterans with OSA who still experience residuals symptoms, despite adequate treatment with CPAP. We will use a cross-over design, where each participant will be exposed to active treatment and sham treatment in a randomize order. We will collect qualitative data from participants regarding the feasibility and acceptability of BLT to guide future testing and implementation of treatment. **SA2** (exploratory): to test the effects of bright light therapy on sleep related functional impairment, quality of life and CPAP-resistant symptoms of sleepiness and depression. Hypothesis: participants will demonstrate improvements in the variables of interest during the four-week active treatment portion of the eight-week crossover study, compared to the four-week sham treatment portion. We will also be able to detect potential treatment carryover effects and inform design decisions for a subsequent larger study. **SA3** (exploratory): to test whether the degree of circadian rhythms regularity (marker of re-alignment) during BLT mediates the effects of BLT on CPAP-resistant symptoms. Hypothesis: the effect of BLT on CPAP resistant daytime symptoms will be exerted through increased regularity of circadian rhythms, assessed via actigraphy. At the completion of this project, we will have generated preliminary data critical to the design and implementation of a larger trial investigating the impact of BLT on CPAP-resistant symptoms of sleepiness and depression, leading to increased functional impairment in OSA patients. If proven effective, this intervention has the potential to improve the lives of many Veterans suffering from OSA who do not find full symptomatic relief with CPAP, by offering a non-pharmacological intervention that is safe, relatively inexpensive and whose implementation demands only a minimal degree of behavioral modification on the patient.

4.0

*** Provide a summary of the background of the study, and explain how this research will contribute to existing knowledge. Describe previous studies that provides a basis to show that the proposed research can be carried out without undue risk to human subjects.**

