SA3: to test the effect of BLT on CPAP resistant daytime symptoms through **reduced variability of circadian rhythms**, assessed via actigraphy. In order to test this, we will first generate relevant rest-activity rhythms (RAR) measures from minute by minute actigraphy measurements collected over seven days: RAR *height* (amplitude, mesor), *timing* (up-mesor, acrophase, down-mesor). *RAR parameters will be modelled from minute-to-minute actigraphy count data using a five-parameter extended sigmoidally transformed cosine model with an anti-logistic function. This model has been shown to fit human RAR data more effectively than a standard cosine curve⁴⁹. The extended cosine model also provides a measure of how well the observed activity data are fitted by the 24-h rhythm model known as the pseudo-F statistic; lower values indicate poorer model fit and suggest an erratic or variable rhythm⁵⁰.* Bivariate analyses of the effect of BLT on variability of circadian rhythms parameters will be compared using repeated measures ANOVA. We will conduct multi-level mixed effects models of each outcome while adjusting for covariates as listed in the primary aim.

ID: Pro00003376

View: 5 Sub-Studies

1.0 * Is there a sub-study or are there sub-studies associated with this study?
There is no sub-study associated with this study.

ID: Pro00003376

View: 6 Study Population Summary

Study Population Summary

1.0 * What is the maximum number of subjects you plan to enroll at VAPHS?
25

2.0 * Do you plan on enrolling patients into different categories:
 Yes No

If yes, please explain:

This is a 2-arm cross-over study with each participant receiving both arms of treatment for 4 weeks each separated by one week of wash-out period to minimize carry over effects. The order of treatment is randomly assigned.

3.0 If this is a multi-site study, indicate the projected total subject accrual:
N/A

4.0 * Please provide a justification for the sample size:
Sample size strictly based on statistical power is not applicable in the proposed pilot trial. This study is mainly aimed at testing feasibility of the proposed design and intervention, rather than hypothesis testing through inferential statistics. The statistics and qualitative data obtained from the proposed pilot trial will be used to inform design adjustments in the subsequent large trial.

ID: Pro00003376

View: 6.1 Study Population

Study Population**1.0 * Check all that apply to describe your study population:**

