If a participant responds to the questionnaires indicating that they are at risk for suicidality, the physician investigator will be consulted. Based on the information obtained, the PI or co-investigators will evaluate suicide risk and decide what level of care is sufficient in conjunction with participants' behavioral health clinician. If the participant does not have a behavioral health clinician, they will be referred to behavioral health for evaluation and treatment.

4.0 * Provide details regarding the nature of each risk using the area provided below:

Risk Name

[View](#) wearing bright light therapy glasses[View](#) Privacy and confidentiality[View](#) Wearing ActiWatch**5.0 * Do you plan on using the research answering service: Yes No**

If yes, please Upload the research answering service form:

6.0 If your study involves a treatment or intervention, please upload the Patient ID Card:[Patient ID card \(0.01\)](#)

ID: Pro00003376 View: 7.1 Risk/Benefit Analysis-Potential Benefits and Alternatives

Risk/Benefit Analysis-Potential Benefits and Alternatives

Describe any potential for direct benefits to participants in this study:

1.0 * Benefit to Subjects:

Hypothesis: The effect of BLT on CPAP resistant daytime symptoms will be exerted through increased regularity of circadian rhythms, assessed via actigraphy. At the completion of this project, we will have generated preliminary data critical to the design and implementation of a larger trial investigating the impact of BLT on CPAP-resistant symptoms of sleepiness and depression, leading to increased functional impairment in OSA patients. If proven effective, this intervention has the potential to improve the lives of many Veterans suffering from OSA who do not find full symptomatic relief with CPAP, by offering a non-pharmacological intervention that is safe, relatively inexpensive and whose implementation demands only a minimal degree of behavioral modification on the patient.

2.0 * Describe alternatives (research or non-research) that are available to subjects if they choose not to participate in this study:

not participate
other research opportunities
VAPHS Standard of Care (patient dependent)

ID: Pro00003376

View: 8 Methods of Recruitment and Retention

Recruitment Methods and Materials used for Retention**1.0 * Select recruitment methods used on this study:**

Name _____

Mail Campaign _____

Referral by independent source _____

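### SA3 (exploratory) is stated as mediation through rhythm regularity, but no stated model links rhythm to symptoms or estimates an indirect effect

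*Combined protocol and SAP*

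**What the plan says.** Section 2 (Study Objectives & Design), item 3.0, labels SA3 exploratory and sets it "to test whether the degree of circadian rhythms regularity (marker of re-alignment) during BLT mediates the effects of BLT on CPAP-resistant symptoms". The accompanying hypothesis is that the effect on daytime symptoms "will be exerted through increased regularity of circadian rhythms, assessed via actigraphy". Section 7.1 (Potential Benefits), item 1.0, repeats that hypothesis, and the SA3 paragraph of section 4.1 (analysis plan) restates the aim as an effect working through less variable rhythms.

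To test this, section 4.1 derives rest-activity parameters and a pseudo-F statistic from seven days of actigraphy, and then names two analyses:

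- The first compares rhythms between treatments: "Bivariate analyses of the effect of BLT on variability of circadian rhythms parameters will be compared using repeated measures ANOVA".
- The second is given in a sentence that also closes the SA2 paragraph, word for word: "We will conduct multi-level mixed effects models of each outcome while adjusting for covariates as listed in the primary aim".

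The primary-aim covariates appear under SA1: "Covariates we will be assessing include demographics (age, sex, race), comorbid conditions, lifestyle behaviors (smoking, alcohol use, substance use), adherence to BLT treatment", then CPAP adherence, depression and hypnotic medication, and healthcare use. The SA1 outcome model has treatment block as predictor of interest, sequence as a covariate and a random subject intercept.

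Section 6 caps enrolment at 25 and describes the study as "mainly aimed at testing feasibility of the proposed design and intervention, rather than hypothesis testing through inferential statistics".

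**The concern.** A mediation claim needs three things: an effect of treatment on the mediator (path a), an association of the mediator with the outcome given treatment (path b), and an estimate of the indirect effect a×b. The plan supplies path a and, through SA1 and SA2, the total effect of BLT on symptoms (path c). It states neither path b nor a×b.

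If BLT improves both rhythm and symptoms, the natural reading of the SA3 results would be that the hypothesis is confirmed. Yet the same pattern arises when light acts on alertness directly and on rhythms separately. The pilot's data are meant to shape a larger trial, so an unsupported statement about mechanism could carry into its design.

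**Working it through.** **Mapping the stated models to the paths**

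| Path | Stated in the plan? | Where |
|---|---|---|
| a: BLT → rhythm | Yes | 4.1, SA3 ANOVA |
| c: BLT → symptoms | Yes | 4.1, SA1 and SA2 models |
| b: rhythm → symptoms, given BLT | No | – |
| a×b: indirect effect | No | – |

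The only sentence that could hold path b is the SA3 mixed-model sentence. If its outcomes are symptoms, it repeats SA2. If they are rhythm measures, it is a covariate-adjusted version of path a. The covariates it refers to include no rhythm measure, so neither reading gives path b.

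**How far the stated tests can mislead (illustration)**

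The plan states no power, alpha or effect size, so there is no figure to reproduce. From the documents: at most 25 participants and a two-sequence crossover. Assumed: two-sided 5% tests, within-person differences (BLT minus sham) with SD 1, equal effects δ on rhythm and symptoms, and 20 completers as a second case. The plan's further covariates are left out.

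*Precision of path a.* The period-adjusted effect has SE = ½·√(1/n₁ + 1/n₂).

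- n = 25 (13 + 12): SE = 0.200, t(23) = 2.069, 95% half-width = 0.414 SD.
- n = 20 (10 + 10): SE = 0.224, t(18) = 2.101, 95% half-width = 0.470 SD.

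*Both tests significant with zero mediation.* With independent measures this probability is the square of the single-test power, taken from the noncentral t with noncentrality δ/SE and n − 2 df. For example, at δ = 0.6 and n = 25 the single-test power is 0.819, and 0.819² = 0.67.

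| δ (SD) | 0.3 | 0.4 | 0.5 | 0.6 | 0.7 |
|---|---|---|---|---|---|
| n = 25 | 9% | 23% | 45% | 67% | 84% |
| n = 20 | 6% | 16% | 32% | 52% | 71% |

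*Can the stated tests tell mediation from none?* Simulated differences: dM = δ + e₁ and dY = (δ − bδ) + b·dM + √(1 − b²)·e₂. The total symptom effect stays at δ whatever b is. There were 4,000 trials per scenario, with a Monte Carlo 95% interval for a×b from 1,500 draws.

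| n, δ, b | Rhythm and symptom tests both significant | Indirect-effect interval excludes 0 |
|---|---|---|
| 25, 0.6, 0 | 67.5% | 5.0% |
| 25, 0.6, 0.3 | 69.0% | 25.9% |
| 25, 0.6, 0.5 | 71.0% | 60.8% |
| 25, 0.6, 0.7 | 73.0% | 82.8% |
| 20, 0.6, 0 | 53.0% | 4.3% |
| 20, 0.6, 0.3 | 54.6% | 19.4% |
| 20, 0.6, 0.7 | 61.4% | 73.0% |
| 25, 0.3, 0 | 8.7% | 1.6% |
| 25, 0.3, 0.7 | 20.2% | 34.4% |

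At δ = 0.6 and n = 25, moving from no mediation to strong mediation shifts the first column by under 6 points and the second by about 78.

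**The case against.** The best case against has four parts.

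- **A third reading.** The SA3 mixed-model sentence names no predictor of interest. A mediator would not normally sit in a list of demographics and medications, so its absence there is weak evidence. The sentence might mean symptom models that use the rhythm measures just derived. This is possible but adds a predictor that the text does not contain, and the identical SA2 sentence points the other way. The uploaded grant application may say more; it is not among the documents, and the analysis plan does not refer to it.
- **Exploratory aim in a pilot.** This is true, and it excuses low power. It does not supply the one path that separates mediation from two parallel effects.
- **No decision rule.** The plan never says that two significant results would establish mediation, so the percentages are not an error rate of this plan. That stands; they only illustrate how little the stated tests discriminate.
- **The remedy looks slightly better than it is.** The indirect intervals used normal draws. With t-based draws, the 26% at b = 0.3 and n = 25 falls to about 21%, and the 19% at n = 20 to about 14%. That also stands, and leaves the conclusion unchanged.

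**Conclusion.** The concern holds. As written, the SA3 analyses cannot support the mediation conclusion that SA3 states. They can count against the pathway: a null BLT-to-rhythm result would be evidence against it, but only to within about ±0.41 SD with 25 completers.

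The structural point needs no assumption about effect size. The percentages do rest on assumed equal effects, 5% tests and no extra covariates, and are there for scale only. The consequence is confined to the mechanism claim; the feasibility aim and SA2 are unaffected. The plan should be changed, because following it as it stands cannot answer the question it poses and either correction is cheap.

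**What to change.** Choose one of two.

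**Option 1: keep the mediation question.** Name one regularity mediator in advance. Pseudo-F is the natural choice because the plan already derives it and ties it to erratic rhythms; log-transform it if skewed. Fix one seven-day window in each treatment block, ending no later than that block's symptom assessment. Then:

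1. Estimate the period-adjusted BLT effect on the mediator (a).
2. Regress the within-person symptom difference (BLT minus sham) on the within-person mediator difference, adjusted for period (b).
3. Report a×b with a bootstrap or Monte Carlo 95% interval, using t-based draws if Monte Carlo.
4. Label the result exploratory, because the mediator is not randomised.

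This costs SAP wording and a small analysis of data already collected. The interval will be wide: with 0.6 SD effects and b = 0.3 it excludes zero in roughly a quarter of trials at 25 completers and a fifth at 20, and somewhat fewer with t-based draws.

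**Option 2: drop the mediation question.** Reword SA3 in sections 2, 4.1 and 7.1 as the effect of BLT on rest-activity rhythm measures, and draw no mediation conclusion. This costs only wording but leaves the mechanism to the larger trial.
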